CCRA	Certified Clinical Research Associate
CLSI	Clinical and Laboratory Standards Institute
CSR	Clinical Study Report
EDC	Electronic Data Capture
FDA SMBG: 2016	Self-Monitoring Blood Glucose Test Systems for Over-the-Counter Use, Guidance for Industry and Food and Drug Administration Staff. Issued 11Oct2016, Food and Drug Administration, USA.
ICF	Informed Consent Form
IRB	Institutional Review Board
ISO 15197:2013 (and EN ISO 15197:2015)	In vitro diagnostic test systems – Requirements for blood–glucose monitoring systems for self-testing in managing diabetes mellitus. Issued 15May2013, International Organization for Standardization, Switzerland. Note: All references to ISO:15197:2013 in this protocol also encompass EN ISO 15197:2015.
PI	Principal Investigator
QRG	Quick Reference Guide
SMBG	Self-Monitoring of Blood Glucose
UADE	Unanticipated Adverse Device Effect
UG	User Guide
YSI	YSI Glucose Analyzer™ (YSI Life Sciences, Yellow Springs, OH)

1.0 Background Information

CONTOUR[®] NEXT is the proposed name of a blood glucose monitoring system (BGMS) consisting of a new meter and marketed CONTOUR NEXT[®] test strip. The development name of the meter is LIGHTNING NEXT. CONTOUR TV3 is the proposed name of a BGMS consisting of a new meter and new V3 test strips. The development name of the meter is THUNDER TV3. The meters can wirelessly transmit BG results using Bluetooth Low Energy to the CONTOUR mobile application that will be available on specified versions of the iOS and Android mobile platforms.

This clinical trial will assess the performance (accuracy) of the CONTOUR NEXT and CONTOUR TV3 meters by lay users enrolled as subjects in the study, and by health care professionals (also called study staff). The trial will follow the requirements and procedures described in FDA Guidance on Self-monitoring Blood Glucose Test Systems: 2016 (FDA SMBG:2016)¹ and ISO 15197:2013 International Standard, Section 8². Results will be evaluated and reported for each of the two BGMS according to each of the two standards (FDA and ISO), for a total of four reports. CONTOUR NEXT results and CONTOUR TV3 results will not be compared to one another.

2.0 Study Objectives

Study objectives 2.1 and 2.2 are in accordance with **FDA SMBG: 2016**, Section C. Method Comparison / User Evaluation, and apply to data collected from **all subjects**: people with diabetes and a smaller number of naïve users (defined as people without diabetes). The objectives apply to both CONTOUR NEXT and CONTOUR TV3 BGMS, and the results from the two meter systems will not be compared to each other.

2.1 Primary Objective (FDA SMBG: 2016), all subjects:

2.1.1 Fingerstick Test: Obtain BGMS performance data in the hands of **lay users with diabetes and naïve users** (without diabetes) from fingerstick capillary blood using Microlet NEXT[®] lancing device.

- **95% of glucose results shall fall within $\pm 15\%$ of laboratory method across the entire tested range**
- **99% of glucose results shall fall within $\pm 20\%$ of laboratory method across the entire tested range**

2.1.2 Samples will adequately span the claimed measuring range. At least ten unaltered samples with blood glucose concentration at the lower limits of the measuring range (less than 80 mg/dl) and at least ten unaltered samples at the upper limit measuring range (greater than 250 mg/dl) will be obtained for each anatomical site (i.e. fingerstick & palm).

¹ Self-Monitoring Blood Glucose Test Systems for Over-the-Counter Use, Guidance for Industry and Food and Drug Administration Staff. Issued 11Oct2016, Food and Drug Administration, USA. (abbreviated FDA SMBG:2016)

² In vitro diagnostic test systems – Requirements for blood-glucose monitoring systems for self-testing in managing diabetes mellitus. Issued 15 May2013, International Organization for Standardization, Switzerland. (abbreviated ISO 15197:2013)

2.2 Secondary Objectives (FDA SMBG: 2016), all subjects:

- 2.2.1 Alternative Site Test (AST): Obtain BGMS performance data in the hands of **lay users with diabetes and naïve users** (without diabetes) from the palm site using the Microlet NEXT lancing device with the AST endcap. Acceptance criteria will be the same as fingerstick 2.1.1.
- 2.2.2 Subject Questionnaire 1: The questionnaire will include statements about the BGMS instructions for use (product labeling) and ease of use of the basic blood testing operations of the meter system. These statements will be given a rating by all of the subjects (1=strongly disagree, 2=disagree, 3=neutral, 4=agree, 5=strongly agree), and frequency distributions will be tabulated. Results will be compared to the following criteria:
- **Acceptance criteria: At least 90% of the applicable statement responses from the questionnaire must be ≥ 3 to pass*.**

Study objectives 2.3.1 and 2.3.4 below are in accordance with **ISO 15197:2013, Section 8**, and apply to data collected **ONLY** from **subjects who have diabetes**. Objectives 2.3.2 and 2.3.3 also apply to subjects who have diabetes. The objectives apply to both CONTOUR NEXT and CONTOUR TV3 BGMS, and the results from the two meter systems will not be compared to each other.

2.3 Secondary Objectives, only subjects with diabetes:

- 2.3.1 Fingerstick Test: Obtain BGMS performance data in the hands of lay users with diabetes using fingerstick capillary blood obtained with Microlet NEXT lancing device.
- **95% of glucose results shall fall within ± 15 mg/dL of laboratory method at glucose concentration < 100 mg/dL and within $\pm 15\%$ at glucose concentrations ≥ 100 mg/dL**
- 2.3.2 Alternative Site Test (AST): Obtain BGMS performance data in the hands of lay users with diabetes using capillary blood from the palm site obtained with Microlet NEXT lancing device with the AST endcap. Acceptance criteria will be the same as fingerstick 2.3.1.
- 2.3.3 Venous Blood Test: Obtain BGMS performance data using venous blood from lay users with diabetes. Acceptance criteria will be the same as fingerstick 2.3.1.
- 2.3.4 Subject Questionnaire 1: The questionnaire will include statements about the BGMS instructions for use (product labeling) and ease of use of the basic blood testing operations of the meter system. These statements will be given a rating by the subjects with diabetes (1=strongly disagree, 2=disagree, 3=neutral, 4=agree, 5=strongly agree), and frequency distributions will be tabulated. Results will be compared to the following criteria:

*This is a “total population” (hypothesis test) requirement for the pool of all subjects.

- **Acceptance criteria: There must be at least a 90% probability that a user would respond with a score of 3 or higher to statements concerning instructions for use or ease of use.****

Study objectives 2.4 below are internal objectives and apply to data collected from all subjects OR subjects who have diabetes, as specified for each objective. The objectives apply to CONTOUR NEXT and CONTOUR TV3 BGMS as noted, and the results from the two meter systems will not be compared to each other.

2.4 Secondary Objectives (internal objectives):

2.4.1 Fingerstick Test (only subjects with diabetes): Obtain BGMS performance data in the hands of lay users with diabetes using fingerstick capillary blood obtained with Microlet NEXT lancing device.

CONTOUR NEXT:

- **95% of glucose results shall fall within ± 10.5 mg/dL of laboratory method at glucose concentrations < 100 mg/dL and within $\pm 10.5\%$ at glucose concentrations ≥ 100 mg/dL****

CONTOUR TV3:

- **95% of glucose results shall fall within ± 12.5 mg/dL of laboratory method at glucose concentrations < 100 mg/dL and within $\pm 12.5\%$ at glucose concentrations ≥ 100 mg/dL****

2.4.2 Study staff test (both BGMS; two analyses, one for all subjects and one for only subjects with diabetes): Obtain BGMS performance data in the hands of trained study staff testing subjects' fingerstick blood obtained with Microlet NEXT lancing device.

- **95% of glucose results shall fall within ± 15 mg/dL of laboratory method at glucose concentrations < 100 mg/dL and within $\pm 15\%$ at glucose concentrations ≥ 100 mg/dL*,****

2.4.3 Subject Questionnaire 2 (both BGMS; only subjects with diabetes): This questionnaire for subjects with diabetes will include statements about user preferences and feedback regarding the features of the BGMS in routine diabetes management. These statements will be given a rating by the subjects (1=strongly disagree, 2=disagree, 3=neutral, 4=agree, 5=strongly agree), and frequency distributions will be tabulated.

- **Acceptance criteria: There are no pass/fail criteria for Questionnaire 2.**

**This is a "total population" (hypothesis test) requirement for the pool of all subjects with diabetes.

3.0 Study Design Summary

This study was designed to satisfy both the *FDA SMBG:2016* and the *ISO 15197:2013, Section 8* requirements. Besides different analysis criteria, the main difference between these regulations is that FDA SMBG:2016 requires that both naïve users (people without diabetes) and people with diabetes are included in the study population. The ISO 15197:2013 standard states that the study population shall be people with diabetes.

The study will be conducted at two clinical sites and enroll a total of approximately 370 lay users. Ten to fifteen percent (10 - 15%) of the enrolled subjects will be people without diabetes and the remaining subjects will be people with diabetes.

For this study, there must be at least 350 total evaluable fingerstick self-test results and at least 350 total evaluable AST palm self-test results for each BGMS, CONTOUR NEXT and CONTOUR TV3. In addition, per FDA SMBG:2016, at least 10 unaltered fingerstick blood samples will be < 80 mg/dL and 10 will be > 250 mg/dL. Subject enrollment will continue until the required evaluable samples are collected.

Sites are not required to replace subjects with diabetes who did not have evaluable venous blood results.

The subjects will be 18 years and older. Each subject will make one visit, lasting approximately 2 hours, to the clinical trial site. Study sessions will be conducted by study staff members who have been trained on all aspects of the protocol, forms, the use of the CONTOUR NEXT and CONTOUR TV3 systems, data collection, and GCP.

All subjects will complete the informed consent process before performing any study procedures.

Procedures - All Subjects

According to a randomization schedule, subjects will be assigned to: 1) use either the CONTOUR NEXT or CONTOUR TV3 meter first, and 2) use one of three test strip lots corresponding to each meter throughout the visit.

The untrained subjects, who have never used either of the systems previously, will be sequestered in such a way that they cannot observe or be influenced by the testing technique of other study participants. They will learn to use the assigned meter by reading the corresponding User Guide (UG) and Quick Reference Guide (QRG). Each subject will perform one fingerstick self-test using a Microlet NEXT or similar lancing device and the assigned meter. Immediately following the subject self-test, a Tenderlett™ or similar device will be used by the study staff on the subject's finger (same hand) to collect a capillary sample for testing on the YSI Glucose Analyzer.

Immediately following the Tenderlett lancing, subjects will lance their palm using the Microlet NEXT lancing device (with AST clear endcap) and will perform a self-test using the meter.

Immediately following the AST test, the staff person will perform a fingerstick test on the subject. All subject self-test results and study staff results will be compared to YSI results from blood obtained from the Tenderlett fingerstick.

Hematocrit will be measured for all subjects.

All Subjects will then complete a questionnaire (Questionnaire 1) to provide feedback on the meter system and instructions for use (UG and QRG).

Procedures - Only Subjects with Diabetes

Subjects with diabetes will be given a venipuncture. The venous blood will be tested by the study staff using the CONTOUR NEXT and CONTOUR TV3 systems, maintaining randomized first meter order, and the YSI lab analyzer. The venipuncture may be performed any time after the subject is enrolled (i.e. completed informed consent and passed inclusion/exclusion criteria).

After all testing is completed, staff will demonstrate to the subjects with diabetes several features of the meter system that would not necessarily be experienced during the brief accuracy testing. These subjects will be given a second questionnaire (Questionnaire 2) to provide feedback about the new features of the system.

Procedures repeated with second BGMS

After completing study procedures for one BGMS, subjects will then repeat all of these procedures using the second BGMS, except the hematocrit and venipuncture procedures. (Hematocrit is measured on a separate instrument and is not meter-specific; venipuncture is performed once and measured on both meters, as previously described.)

4.0 Subject Recruitment, Inclusion/Exclusion Criteria

Subject Recruitment: At least 370 subjects will be enrolled into the study. These will be people with diabetes (type 1 or type 2) and a smaller number, 10 - 15%, without diabetes. The subjects will be members of the local communities.

4.1 Inclusion Criteria:

- 4.1.1 Males and females, 18 years of age and older
- 4.1.2 Ability to speak, read and understand English. Subjects must demonstrate ability to read a paragraph from the first page of the UG to qualify for the study.
- 4.1.3 Willing to complete all study procedures

4.2 Exclusion Criteria:

- 4.2.1 Hemophilia or any other bleeding disorder
- 4.2.2 Pregnancy (self-reported)
- 4.2.3 Physical, visual or neurological impairments that would make the person unable to perform testing with the BGMS.
- 4.2.4 Previous participation in a blood glucose monitoring study using the Ascensia CONTOUR NEXT or CONTOUR TV3 BGMS.
- 4.2.5 Working for a medical laboratory, hospital or other clinical setting that involves training on or clinical use of blood glucose monitors.

4.2.6 Working for a competitive medical device company, or having an immediate family member or someone who is not a family member but is living within the household of someone who works for such a company.

- Immediate family members are the subject's parents, spouse, children, and siblings, including the parent's spouse; step-children and adopted children and their spouses.
- A competitive medical device company is a company that provides a medical device or components of a device that is related to diabetes.

For example, people who are not eligible are those who work for companies that create or manufacture the following (or a company that is in a partnership with a company that provides such devices): lancing devices, blood glucose monitoring systems, continuous glucose monitoring systems, insulin pens, or systems related to the measurement of HbA1c.

People who are eligible are those who work for companies associated with products such as wound dressings, medications or dietary products.

4.2.7 A condition, which in the opinion of the investigator or designee, would put the person or study conduct at risk. The reason for exclusion will be clearly documented by investigator or designee on the subject disposition form.

4.3 **General Enrollment Details - Combined across sites**

4.3.1 The following additional population criteria are study goals with each site recruiting to meet these goals:

1. At least 70% of subjects will be younger than age 65.
2. Ten to fifteen % (10-15%) of subjects will be people without diabetes.
3. At least 20% of subjects (with diabetes) will have type 1 diabetes.

4.3.2 No laboratory tests (e.g., pregnancy) are required to assure qualification. Subjects' verbal responses will be accepted and recorded on forms which will serve as source documents for the electronic data capture (EDC) system.

4.3.3 Subject venipuncture may be performed at any time during the subject visit.

5.0 Materials and Methods

5.1 **Resources Supplied by Investigational Site**

5.1.1 **Staffing**

1. Principal Investigator and, as needed, Sub-Investigator(s)
2. Study Coordinator

3. Two or more study staff to conduct the study
4. Staff person(s) to measure hematocrit, prepare samples for YSI analysis, and perform YSI analysis of venous and capillary blood (plasma) and serum controls (per site: sponsor agreement)
5. Data entry person for EDC data entry (Note: This requires EDC training.)

5.1.2 Other

1. Final informed consent forms (ICF), and other necessary supporting documents, as appropriate
2. Computer with internet connection for site and monitor access to EDC system
3. Facility with adequate space for conducting all testing. Site facilities for conducting subject visits must allow sufficient privacy so subjects cannot observe other subjects' BGMS testing procedures. Testing area must also be conducive to allowing subjects to focus on testing (i.e. background distraction to be kept to a minimum).
4. YSI analyzers, reagents, and supplies
5. Supplies to treat any hypoglycemic events
6. Venipuncture supplies
7. Laboratory supplies including: disposable pipets, gloves, alcohol wipes, band aids, gauze, parafilm, disposable benchtop covers
8. Tenderlett™ or similar single-use lancing device
9. Micro collection tubes with lithium heparin anticoagulant (no gel separator)
10. Hand warmers
11. Biohazardous bags and sharps containers

5.2 Resources Supplied by Ascensia

5.2.1 Staffing

1. Ascensia Study Manager
2. Study Monitor(s)

5.2.2 Materials

1. Protocol, EDC system, paper case report forms (CRF) and questionnaires, as needed
2. ICF template
3. CONTOUR NEXT meters (Note: Meters will have Bluetooth turned ON throughout the study.)
4. CONTOUR NEXT User Guides (UG) and Quick Reference Guides (QRG)
5. CONTOUR NEXT test strips - 3 lots labeled as RED, GREEN, BLUE (R, G, B). A minimum of 10 vials of test strips per lot will be provided.

6. CONTOUR TV3 meters (Note: Meters will have Bluetooth turned ON throughout the study.)
7. CONTOUR TV3 UGs and QRGs
8. V3 test strips – 3 lots labeled as RED, GREEN, BLUE (R, G, B). A minimum of 10 vials of test strips per lot will be provided.
9. CONTOUR NEXT/CONTOUR TV3 (Normal level) control solution
10. Microlet NEXT lancing device systems including clear, AST endcap. (All subjects will be provided new lancing devices and lancets; lancing devices will not be shared among subjects.)
11. Thermometer / hygrometer
12. Statspin™ microcentrifuge and tube rotors
13. Microhematocrit tube reader (or equivalent hematocrit measurement system), hematocrit rotors, sealant
14. Microhematocrit tubes without anticoagulant (for testing venous blood)
15. Microhematocrit tubes with anticoagulant (for testing capillary blood)
16. Clocks with 24-hr time option
17. Ascensia serum glucose traceability controls (four levels)
18. Disposable microtubes, disinfectant wipes for meters
19. Package delivery forms and envelopes (UPS or Fed Ex)

5.3 Site Staff Pre-Study Orientation

The Ascensia Study Manager, or designee, will review all study documents, procedures (including procedures for data collection and management), GCP, and usage of the CONTOUR NEXT and CONTOUR TV3 BGMS with the site staff. All site staff involved in subject testing sessions will successfully perform at least one control solution test with each of the two BGMSs. Study-specific EDC training will also be provided to study staff as necessary.

5.4 Safety and Disinfection Procedures:

1. Universal precautions will be used throughout the study.
2. Only study staff will perform disinfection procedures. Subjects will not perform disinfection.
3. A new CONTOUR NEXT and CONTOUR TV3 meter will be provided to each subject. At the end of the subject's visit, the meters will be disinfected and stored until they are returned to Ascensia.
4. A new Microlet NEXT or similar lancing device will be provided to each subject. At the end of the subject's visit, the lancing device will either be discarded or offered to the subject to take home.
5. The lancets used in the study (Tenderlett and Microlet lancets) will be disposed of in a biohazard sharps container after use.

6. Microlet lancets must be changed for each lancing by the subject. (Insert, remove, and discard into sharps container.)
7. Disposable exam gloves will be worn by site staff during study procedures where the risk of transmission of disease is present. These procedures include performing blood glucose measurements, sample processing, and laboratory procedures involving blood samples. A new pair of gloves will be used when working with each subject and will be changed between subjects.
8. All test strips are single-use and will be appropriately discarded after use.
9. Disposable bench top covers should cover the work area and must be changed between subjects.
10. A marketed BGM device may be used for determining the subject's glucose level during the study as needed for safety reasons or to ascertain the glucose level for study reasons. The meter will be disinfected after use with each subject.

5.5 Study Staff Quality Control Testing of Meters

Prior to enrollment of the first subject, the study staff will perform testing with Contour normal level control solution on all CONTOUR NEXT and CONTOUR TV3 meters. All staff control testing will be done out of sight of the study subjects. If the results are out of range, troubleshooting will be performed (see meter UGs) and the test will be repeated. If the meter tests are out of range after troubleshooting is complete, the meter will be removed from the study. This will be documented on the Problem Reporter form, as described in Section 5.15 'Device Problem Reporting'.

5.6 Subject Enrollment

- 5.6.1 At least 185 untrained subjects, who have never previously used the Ascensia CONTOUR NEXT or CONTOUR TV3 BGMS, should be enrolled into the study at each site in order to have a total of at least **350 evaluable fingerstick** and **350 evaluable AST palm** blood results for each BGMS. Of the fingerstick blood samples, 10 samples should be < 80 mg/dL and 10 samples > 250 mg/dL (by YSI assay). If this requirement is not achieved with 350 subjects, additional subjects should be enrolled to meet this fingerstick requirement. Note that the goal at each site should be approximately five capillary fingerstick blood results < 80 mg/dL and five > 250 mg/dL.
- 5.6.2 The site study staff will perform the following when the subject arrives at the clinical trial site:
 1. Complete the informed consent process.
 2. Assign a unique number to each subject.
- 5.6.3 The study staff will document subject demographics (including both screen-failed and enrolled subjects), diabetes history, medical conditions and medications information.

Subjects will also be asked when they last ate, took diabetes medications, and performed vigorous exercise.

5.6.4 If the subject does not have diabetes, the outside of the subject folder will be labeled to indicate that venipuncture should NOT be performed.

5.6.5 According to a randomization schedule, subjects will be assigned to: 1) use either the CONTOUR NEXT or CONTOUR TV3 meter first, and 2) use one of three test strip lots corresponding to the meter throughout the visit (lot R, B, or G).

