11.7 Glucose distribution

The distribution of YSI glucose and a histogram (combined sites) for both capillary and venous blood will be provided. The mean, median, minimum, maximum, and standard deviation will be computed for glucose distributions, for subjects with diabetes and for all subjects, by site and for both sites combined.

In addition, the number of capillary samples with concentrations <80 and > 250 mg/dL will be reported.

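### Objective 2.1.2 sets a 10 low / 10 high minimum for palm as well as fingerstick, but the enrolment rule in 3.0 and 5.6.1 secures it for fingerstick only

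*Combined protocol and SAP*

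**What the plan says.** **Objective.** Section 2.1.2, under the FDA primary objective, has two halves. For the low band: "At least ten unaltered samples with blood glucose concentration at the lower limits of the measuring range (less than 80 mg/dl". For the high band, with the counting unit: "greater than 250 mg/dl) will be obtained for each anatomical site (i.e. fingerstick & palm". The introduction to section 2.0 adds: "The objectives apply to both CONTOUR NEXT and CONTOUR TV3 BGMS".

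**Enrolment rule.** Section 3.0 asks for 350 evaluable fingerstick and 350 evaluable palm results for each meter system, then adds that "at least 10 unaltered fingerstick blood samples will be < 80 mg/dL and 10 will be > 250 mg/dL". It says that enrolment goes on until the required evaluable samples are in hand. Section 5.6.1 repeats the two totals of 350 and continues: "Of the fingerstick blood samples, 10 samples should be < 80 mg/dL and 10 samples > 250 mg/dL (by YSI assay". If that is not achieved with 350 subjects, "additional subjects should be enrolled to meet this fingerstick requirement". Each clinic aims for about five low and five high fingerstick results.

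**Reporting.** Section 11.7 says that "the number of capillary samples with concentrations <80 and > 250 mg/dL will be reported".

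**The concern.** The objective and the rule meant to deliver it count different things. The objective counts by anatomical site and names the palm. The rule that decides when recruitment may stop names only fingerstick, counts by YSI value rather than by evaluable meter result, and does not repeat the per-meter qualifier that it attaches to the totals of 350.

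A clinic that follows 5.6.1 to the letter could close enrolment while a meter has fewer than ten palm results in a band. The FDA report for that meter would then fall short of the glucose coverage stated in its own objective. Section 11.7 would not show the shortfall, because its count is of capillary samples with no finger/palm split. Once enrolment has closed, a missing band can be filled only by reopening it.

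**Working it through.** **1. What the rule covers.** The plan's own figures reproduce: 2 clinics × 5 = 10 per band, and 2 × 185 = 370 enrolled. The documents give no derivation of the ten.

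Objective 2.1.2 has 2 bands × 2 anatomical sites × 2 meters = 8 cells, each needing at least ten. Sections 3.0 and 5.6.1 name fingerstick low and fingerstick high, which is 4 cells if read per meter. No reading covers the 4 palm cells. The palm total of 350 is a count at any glucose level and fixes nothing within a band.

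**2. When palm falls short of finger.** Palm and fingerstick results are compared with the same capillary YSI value (5.9.1), and the palm test goes ahead only after an adequate YSI sample (5.7.2). A finger sample in a band therefore has a palm partner in that band unless the palm result is lost. A palm result is non-evaluable if more than 15 minutes separate it from centrifugation (5.7.2), or if it follows eating or medication (5.9.13). Eating is allowed at any time to avoid or treat hypoglycemia, and the palm test comes after the fingerstick, so some of this loss may concentrate in the low band.

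**3. Risk if enrolment stops at exactly ten.** Let d be the palm loss rate, which the documents do not give. With independent losses, P(fewer than 10 palm results | 10 finger samples) = 1 − (1 − d)^10. One value of d, 5.4%, is borrowed from the enrolment allowance, 1 − 350/370; that allowance is not a stated palm loss rate.

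| Assumed palm loss d | P(palm < 10), one band, one meter | Finger samples for at least 95% assurance of 10 palm results |
|---|---|---|
| 1% | 9.6% | 11 |
| 2% | 18% | 11 |
| 5.4% | 43% | 12 |
| 10% | 65% | 13 |
| 20% | 89% | 16 |

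For d = 2%: 1 − 0.98^10 = 1 − 0.817 = 0.183. For d = 5.4%: 1 − 0.946^10 = 1 − 0.574 = 0.426.

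**4. Risk before the band count is known.** Stopping at exactly ten is the worst point. With 350 evaluable finger results for a meter and a share q of samples in the band, the finger count K is binomial(350, q). If K < 10, enrolment runs on to ten. The risk is the sum over k of P(K = k) × P(binomial(max(k, 10), 1 − d) < 10). The documents do not give q, so a range is shown.

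| Share in band q (expected 350q) | d = 2% | d = 5.4% | d = 10% | d = 20% |
|---|---|---|---|---|
| 2% (7) | 17% | 39% | 61% | 85% |
| 3% (10.5) | 10% | 24% | 39% | 62% |
| 4% (14) | 3.3% | 8.5% | 15% | 30% |
| 5% (17.5) | 0.7% | 2.0% | 3.9% | 10% |
| 6% (21) | 0.1% | 0.3% | 0.7% | 2.6% |

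The separate minimum of 350 palm results lowers these a little. Running the same sum with 370 finger results, which at 5.4% loss yield about 350 palm results, gives 38%, 21%, 6.3%, 1.2% and 0.2% in place of the d = 5.4% column. The pattern is the same.

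**The case against.** **The palm gap is mostly formal.** Palm shares the fingerstick YSI value, 350 palm results per meter are required anyway, section 3.0 says enrolment continues until the required evaluable samples are collected, and 2.1.2 remains a stated requirement. The first two points stand as limits on size: overall palm loss is constrained, and the risk is low when the bands are well filled. They do not close the gap, because losses within a band are not counted. The sentence in 3.0 does not close it either, since the list before it names only fingerstick for the band minimum.

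**A stronger per-meter reading.** Each subject gives one capillary YSI sample per meter, so a reader might infer that ten samples pooled over meters could come from five subjects, leaving five per meter. The documents do not support treating this as the rule. In 5.6.1 the sentence just before the band minimum ends with the per-meter qualifier, so the natural referent is the 350 fingerstick results of each meter. What remains is a qualifier worth repeating.

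**The count in 11.7.** A reader might also take this as one figure pooled over meters. The opening of section 11.0 makes the analyses for each meter independent, so the count is already per meter. Only the finger/palm split is missing.

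**Effect on pass/fail.** A reader might argue that sparse bands weaken the accuracy test itself. The FDA accuracy criteria apply across the whole tested range and no band has its own criterion, so the planned critical values and operating characteristics are unaffected.

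**Conclusion.** The point holds for the palm. Section 2.1.2 conflicts with 3.0 and 5.6.1, and the conflict bears on when enrolment may stop. The missing per-meter wording is a clarification to make in the same edit.

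The size depends on two quantities that the documents do not give. At an assumed 5.4% palm loss, the chance of closing with fewer than ten palm results in a given band for a given meter is 39% if 2% of samples fall in that band, 8.5% at 4%, and 2% at 5%. At 5% or more in the band, the risk stays below 4% for losses up to 10%, but reaches 10% if a fifth of palm results are lost. These figures assume independent losses at the same rate in every band; if eating to avoid or treat hypoglycemia removes later results, the low band would do worse. The consequence is incomplete coverage against a stated objective, not a wrong accuracy conclusion.

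**What to change.** In 3.0 and 5.6.1, state the minimum as ten evaluable meter/YSI pairs below 80 mg/dL and ten above 250 mg/dL, for fingerstick and for palm, for each meter system. That is eight counts. Make the decision to stop enrolment depend on all eight. In 11.7, add the finger/palm split to the per-meter count. Counting palm directly avoids having to assume a palm loss rate.

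If the fingerstick-only rule is what the sponsor intends, restate 2.1.2 to match it instead.

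The cost is wording and a running tally. Because palm shares the fingerstick YSI value, few extra subjects should be needed: in the first table, 12 finger samples in a band rather than ten give at least 95% assurance at 5.4% loss. The small downside is that recruitment at the extremes may stay open slightly longer.
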